This study is a prospective observational study. Three drops of heel peripheral blood samples were collected from 2000 newborns, and 24 genes of 29 NHB-related genetic diseases were analyzed. All dry blood spot samples that met the inclusion criteria could be included in the genetic analysis. At the same time, the clinical data of these 2000 newborns were collected, and the daily jaundice monitoring at home was performed using the percutaneous jaundice meter (YSJ-20). The data were synchronized to the mobile phone jaundice follow-up doctor assistant small program for storage statistics. The family members can view the jaundice risk level and obtain free doctor consultation in the small program.

The purpose of this study is to study the carrying rate of pathogenic genes of common hereditary jaundice diseases in newborns, to understand whether there is a difference in the carrying rate of pathogenic genes in different degrees of jaundice, to explore whether there is a difference in the degree of jaundice carrying multiple and single jaundice pathogenic genes, and to analyze the correlation between gene polymorphism and clinical manifestations (phenotypic polymorphism) of neonatal hyperbilirubinemia, so as to evaluate the feasibility of jaundice gene screening program in the detection of jaundice-related genetic metabolic diseases.

Based on the 'Classification Criteria and Guidelines for Genetic Variation (2017)', the variation pathogenicity of genetic testing is divided into five categories : known pathogenic, possible pathogenic, unclear significance, possible benign and benign. In this study, known pathogenic and possible pathogenic are classified as positive results. The pathogenicity of the mutation site is mainly based on the pathogenic mutation database and the latest literature reports.

The classification criteria of jaundice were based on the American Academy of Pediatrics (AAP) 2022 edition of neonatal hyperbilirubinemia management guidelines for gestational age ≥ 35 weeks and the latest version of 2023 guidelines to interpret the management of neonatal hyperbilirubinemia-the diagnosis and intervention criteria of neonatal hyperbilirubinemia in the American Academy of Pediatrics and multi-national clinical management guidelines. The 2000 neonates were divided into 500 cases of non-

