significant hyperbilirubinemia ($TSB / TCB < 205\text{umol} / \text{L}$), 500 cases of significant hyperbilirubinemia ($205\text{umol} / \text{L} \leq TSB / TCB < 342\text{umol/L}$), 500 cases of severe hyperbilirubinemia ($TSB/TCB \geq 342\text{umol/L}$) and 500 cases of extremely severe hyperbilirubinemia ($TSB/TCB \geq 428\text{umol} / \text{L}$).

4. Inclusion criteria

- (1) Informed consent of parents or guardians ;
- (2) Age : 1-28 days, gestational age ≥ 35 weeks ;
- (3) Birth weight ≥ 2.5 kg and < 4 kg.

5. Excluded criteria

- (1) Neonatal data with unclear clinical basic information ;
- (2) Lack of traceability core information data ;
- (3) data that the test results cannot be analyzed and interpreted ;
- (4) Sample collection is not qualified and unwilling to cooperate with re-sampling.
- (5) Newborns with severe deformity and severe lethal inherited metabolic diseases

6. termination criteria

- (1) The family members of the newborn included in the study requested termination at any time ;
- (2) The relevant management departments require termination.

7. outcome index

Through the comprehensive analysis of genetic variation information and jaundice clinical data, the carrying rate of pathogenic genes of common hereditary jaundice diseases in newborns was counted, and the difference of carrying rate of pathogenic genes in different degrees of jaundice was understood. To explore whether there is a difference in the degree of jaundice carrying multiple and single jaundice pathogenic genes, and to analyze the correlation between gene polymorphism and clinical manifestations (phenotypic polymorphism) of neonatal hyperbilirubinemia.

8. Grouping and sample size

This study is a prospective observational study. According to the positive mutation rate of NHB-related genes in neonatal hyperbilirubinemia, P is about 30 %, the test level α

= 0.05 and the allowable error $\delta = 2 \%$, n (sample size) = ($U\alpha / \delta$) $2 * p * (1 - P) \approx$ 2000 cases. A total of 2000 neonates were included, including 500 cases of non-significant hyperbilirubinemia ($TSB / TCB < 205\text{umol} / L$) ; (2) 500 cases of significant hyperbilirubinemia ($205\text{umol} / L \leq TSB / TCB < 342\text{umol} / L$) ; (3) 500 cases of severe hyperbilirubinemia ($TSB / TCB \geq 342\text{umol} / L$) ; (4) Extremely severe hyperbilirubinemia 500 cases ($TSB / TCB \geq 428\text{umol} / L$) .

9. Recruiting

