This study will recruit subjects in the outpatient and inpatient departments of pediatrics, neonatology, and obstetrics in the South China Neonatal Genetic Screening Alliance (including cooperation units of 49 hospitals).

10. Clinical evaluation index

- (1) The carrying rate, positive rate, negative rate and high-frequency mutation sites of common NHB-related gene mutation sites in neonates ;
- (2) The difference in the carrying rate of NHB-related pathogenic genes in neonates with different degrees of jaundice ;
- (3) The difference of jaundice degree between carrying multiple and single jaundice pathogenic genes ;
- (4) Gene-gene interaction and genotype-phenotype correlation.

11. Methods

11.1 gene sequencing

A total of 24 genes were included in 29 NHB-related genetic diseases, including bilirubin metabolic disorders, congenital bile acid synthesis or transport disorders, red blood cell metabolic defects, lipid metabolic abnormalities, and metal metabolic abnormalities. The detected genes included ABCB11, ABCB4, ABCC2, ABCD3, ACOX2, AKR1D1, AMACR, ATP7B, ATP8B1, CYP7B1, G6PD, GBA, HBB, HSD3B7, JAG1, NOTCH2, NPC1, NPC2, NR1H4, SLC10A1, SLC25A13, SMPD1, TJP2 and UGT1A1. Gene and genetic disease related information refer to OMIM and Orphanet database.

Target gene sequence capture and library construction. Three drops of heel peripheral

blood were collected by filter paper, and genomic DNA was extracted by magnetic bead method. The target gene sequence was captured by multiplex PCR amplification method, covering all exon regions and adjacent intron regions ($\pm 50\text{bp}$) of the target gene. A total of 900 amplicons were designed for 24 genes and completed in two amplification systems. The target sequence library was obtained after amplification-purification-re-amplification-re-purification. The library was quantified using a Qubit[®] 3.0 fluorescence quantitative instrument (Thermo Fisher Scientific), and the library length was determined using an Aglient 2100 biological analyzer (Agilent) (228-378 bp).

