High-throughput sequencing and bioinformatics analysis. The library was diluted, added sequencing primers, and sequenced on the Illumina NextSeq 550 platform (PE150). The effective sequencing data were aligned to the human reference genome (Human _ B37) by BWA (Burrows-Wheeler Aligner) software. GATK (Genome Analysis ToolKit) was used to analyze the variation information, and ANNOVAR software was used to annotate the variation, including the annotation information of dbSNP database, Thousand Human Genome Project and other existing databases. The annotation content covers population frequency, mutation type, function prediction (SIFT, Polyphen2, Mutation Taster, etc.), HGMD, Clinvar and other pathogenic classification information. Based on the ' Classification Criteria and Guidelines for Genetic Variation (2017) ', the pathogenic interpretation of genetic variation was divided into five categories : ' pathogenic ', ' possible pathogenic ', ' unclear significance ', ' possible benign ' and ' benign '. Among them, ' pathogenic ', ' possible pathogenic ' and ' unclear significance ' were included in the statistics of test results.

Validation of positive loci. For children with autosomal recessive double heterozygosity and children with autosomal dominant single heterozygosity, Sanger sequencing was used to verify the loci of their parents.

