11.2 Information and data collection

Researchers should truthfully fill in the test results of the subjects and other relevant information, and ensure that the information is true and reliable. The specific

information and data to be collected are as follows :

(1) Sign informed consent ;

(2) Jaundice gene detection : Take out the special filter paper blood collection card, disinfect with alcohol and dry the heel blood collection site, collect heel peripheral blood, drop three drops on the filter paper.

(3) Detection of jaundice value by percutaneous jaundice meter : The family members of the subjects rented the percutaneous jaundice meter for free under the guidance of the doctor, and used the ' single measurement mode ' to measure the forehead, chest and inner thigh of the subjects every day for a total of 2 weeks.

(4) Collect demographic characteristics : screening number, name, gender, gestational age, date of birth, birth weight, body length, head circumference, mode of conception, Apgar score and parental information ;

(5) Perinatal information : parity, parity, mode of delivery, fetal membranes, amniotic fluid, placenta, umbilical cord, intrauterine distress, group B streptococcal infection, pregnancy complications such as gestational hypertension, diabetes, etc.

(6) Jaundice information : parents and newborns blood type, hemolysis three tests, feeding methods, percutaneous jaundice value, jaundice treatment and related test results ;

(7) Gene detection results : Collect gene analysis results, notes, etc.

12. Statistical processing

IBM-SPSS 26.0 statistical software and R language (Version 4.1.0) were used for statistical analysis of the test results. The carrying rate of common NHB-related gene mutation sites in neonates was counted, and the differences in the carrying rate of NHB-related pathogenic genes in neonates with different degrees of jaundice were compared. To explore the difference in the degree of jaundice carrying multiple and single jaundice-related genes. The measurement data were expressed as mean \pm standard deviation ($x \pm s$), and the t test was used for comparison between groups. The count data were expressed as values or rates (%), and the chi-square test was used for comparison between groups. Unconditional logistic multivariate regression analysis

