The coding table for recording neonatal information and research will be kept by the researcher (PI) in a locked file cabinet or in a password-protected database. Only researchers and their authorized researchers have the right to access the coding table.

The coding table that records the name of the hospital and the institution identification number will be saved by the research team in a locked file cabinet, which is only limited to access by limited research members. The identity of each subject of observation should be kept confidential in research reports and related publications.

18. Research progress

September 01, 2023 to March 31, 2024: The samples were grouped and tested : (1) contact parents for informed consent ; (2) Collect 3 drops of heel peripheral blood samples, extract genomic DNA by magnetic bead genomic DNA extraction kit, and detect the samples by high-throughput sequencing technology ; (3) Collect neonatal clinical data and daily percutaneous bilirubin levels through the hospital inpatient system and the ' percutaneous jaundice instrument home monitoring + software doctor-patient interconnection ' method.

April 01, 2024 to June 30, 2024: Data analysis : (1) Statistics of neonatal common jaundice-related gene screening results : the positive rate of common jaundice gene screening (common positive disease cases, high-frequency pathogenic sites), the carrying rate of pathogenic mutations, the carrying rate of pathogenic genes with different degrees of jaundice, and the degree of jaundice carrying multiple and single jaundice pathogenic genes. (2) Combined with clinical data and data uploaded by

transcutaneous jaundice meter : Correlation analysis and comparison of jaundice-related gene detection results and jaundice clinical data to evaluate the feasibility of jaundice gene detection for neonatal hyperbilirubinemia screening.

July 01, 2024 - December 31, 2024: Write the conclusion report, complete the paper, submission and publication work.

19. Reference

- [1] Kong Yuanyuan, Zhang Yumin, Ding Hui. General situation and progress of neonatal disease screening. Chinese Journal of Preventive Medicine. 2011 , 45(10):954-956. DOI:10.3760/cma.j.issn.0253-9624.2011.10.023.
- [2] ZHANG Weiran, ZHAO Zhengyan. Research progress of neonatal disease gene screening. Chinese Journal of Pediatrics.2020 , 58(12):1033-1037. DOI:10.3760/cma.j.cn112140-20200614-00620.

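### Variant classification is not masked to jaundice severity, not explicitly fixed once per variant, and not locked before linkage to bilirubin data

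*Combined protocol and SAP*

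**What the plan says.** **Groups and comparison.** Section 8 sets four severity groups by TSB/TCB: "A total of 2000 neonates were included, including 500 cases of non-significant hyperbilirubinemia" and 500 in each of the other three. The second evaluation index in section 10 is "The difference in the carrying rate of NHB-related pathogenic genes in neonates with different degrees of jaundice". The third and fourth indices (multiple against single pathogenic genes, and genotype with phenotype) use the same variant calls. Section 12 compares rates by chi-square and adds logistic regression.

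**What counts as positive.** Section 3: "In this study, known pathogenic and possible pathogenic are classified as positive results". In section 11.1, "the pathogenic interpretation of genetic variation was divided into five categories", and there the statistics of test results also take in *unclear significance*.

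**How a call is made.** Section 3: "The pathogenicity of the mutation site is mainly based on the pathogenic mutation database and the latest literature reports". Section 11.1 lists the annotation used: population frequency, mutation type, function predictors, HGMD and ClinVar.

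**Timing.** Section 18 opens the period from 1 September 2023 to 31 March 2024 with "The samples were grouped and tested". Three steps follow: consent; blood sampling and sequencing; then "Collect neonatal clinical data and daily percutaneous bilirubin levels through the hospital inpatient system", together with home monitoring. Under section 11.2(3), families use the home meter "to measure the forehead, chest and inner thigh of the subjects every day for a total of 2 weeks".

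**Coding and locking.** Sections 13 and 17 give each infant a unique number and keep the coding table for the researchers and those they authorize. Section 13 locks the database after all queries are resolved.

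**The concern.** The exposure in the main comparisons is a judged category. Where the evidence on a variant is thin, someone must decide whether it is *possible pathogenic* (positive) or *unclear significance* (not positive under section 3). If that person knows the infant's bilirubin group, the same evidence may be read more generously in a severe infant. Exposure would then be partly defined by outcome, and a difference in carriage could appear where none exists.

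The plan has none of the three usual safeguards: masking of the interpreter, an explicit rule of one class per variant, and a lock on calls before linkage. The study numbers are a privacy measure and are not described as hiding severity. The section 13 lock comes at the end, after queries, so it does not protect calls made while bilirubin data were visible. At stake is the credibility of the severity comparison, which is meant to inform whether gene screening for jaundice is feasible.

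**Working it through.** **1. The plan's own figure.** Section 8 uses P = 0.30, error 0.02 and alpha = 0.05. With two-sided z = 1.96, n = (1.96/0.02)² × 0.30 × 0.70 = 9604 × 0.21 = 2016.8, which agrees with the stated figure of about 2000. This is a precision calculation for one proportion. It does not depend on masking and would not change if masking were added.

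**2. Can severity be known at interpretation?** Section 18 puts grouping, sequencing and bilirubin collection in one seven-month period. Its opening words mention grouping first, but its numbered steps put sequencing before clinical data. With two weeks of home readings, some infants' final group may be unknown when the spot is taken. On the other hand, filling four groups of 500 presumably needs severity to be tracked during recruitment (an inference). So the documents neither state nor exclude that severity is known when variants are read. The risk does not need grouping to come first; it needs only that knowledge.

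**3. Which variants are exposed?** Section 3 speaks of the mutation site. A class given once to a site applies equally to its carriers in all four groups. Exposure is therefore limited to rare or novel variants, seen in very few infants, that lie near the line between *possible pathogenic* and *unclear significance*.

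**4. Which counts are exposed?** Counts using the section 3 definition are. In a count that also includes *unclear significance* (section 11.1), moving a variant across that line changes nothing. Sections 10 and 12 do not say which count the between-group test uses.

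**5. Size, as an illustration.** All inputs except n = 500 per group are assumptions: a clear positive in 25% of every group; a borderline variant in a further fraction b of every group; borderline variants called positive at rate c in the most severe group and 0.20 in the comparator. There is no true difference.

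- Rates: p₁ = 0.25 + b·c and p₂ = 0.25 + 0.20·b.
- Rejection probability, with d = p₁ − p₂: Φ((d − 1.96·s₀)/s₁) + Φ((−d − 1.96·s₀)/s₁), where s₀ = √(2p̄(1−p̄)/500), p̄ = (p₁ + p₂)/2, and s₁ = √((p₁(1−p₁) + p₂(1−p₂))/500).

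For b = 0.10 and c = 0.50: p₁ = 0.30, p₂ = 0.27, and the odds ratio is (0.30/0.70)/(0.27/0.73) = 1.16. With s₀ = 0.02855 and s₁ = 0.02853, the terms are Φ(−0.910) + Φ(−3.012) = 0.183.

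For b = 0.10 and c = 0.25: p₁ = 0.275, p₂ = 0.27, and the odds ratio is 1.03. With s₀ = s₁ = 0.02816, the terms are Φ(−1.782) + Φ(−2.138) = 0.054.

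Odds ratio and rejection probability over a range of both assumptions:

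| Call rates | b = 5% | b = 10% | b = 15% |
|---|---|---|---|
| 25% vs 20% | 1.01; 5.1% | 1.03; 5.4% | 1.04; 5.8% |
| 35% vs 20% | 1.04; 5.8% | 1.08; 8.3% | 1.12; 12.3% |
| 50% vs 20% | 1.08; 8.3% | 1.16; 18.3% | 1.24; 34.1% |

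**6. Four-group check.** Assume a true 30% everywhere and a shift of 3 points in the two most severe groups. Then p̄ = 0.315 and the noncentrality is 500 × 4 × 0.015²/(0.315 × 0.685) = 2.09. On 3 degrees of freedom a nominal 5% chi-square rejects 19.9% of the time. A 1-point shift gives 6.4%.

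**The case against.** The strongest reply is that no listed input to classification is the infant's own jaundice. The inputs are databases, literature, frequency and prediction software, so the bias hangs on the word *mainly* in section 3. Whether the cited 2017 classification guideline admits a patient's phenotype as evidence cannot be settled from these documents. This stands in part. It narrows the risk but does not exclude it, because the plan gives no rule for weighing the inputs and leaves room for others.

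Second, classification is described by site, so one class per variant is the natural reading. That is fair, and it is why the point is confined to rare or novel borderline variants. It is still not written as a rule for the cohort.

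Third, the size depends on an assumed gap in call rates. This stands in full: with a small gap, rejection is close to nominal.

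Two stronger readings are tempting and should not be drawn:

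- A reader might infer from section 18 that samples are grouped by severity before they are tested. The phrase does not fix an order, and the steps beneath it list sequencing before bilirubin collection.
- A reader might infer that the high-frequency sites proposed for screening would carry the same bias. By definition such sites recur in many infants, and the mechanism concerns variants seen in very few.

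**Conclusion.** The gap is real and limited. The plan does not mask severity from those who classify variants, does not explicitly require one class per distinct variant, and does not lock calls before linkage. The comparisons exposed are those that use the section 3 definition of positive, and the variants exposed are rare or novel ones near the borderline.

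The documents give neither the share of infants with such variants nor any gap in call rates, so the size is unknown and may be negligible. With 10% borderline carriers and no true difference, the false-positive rate of a nominal 5% test of 500 against 500 runs from about 5.4% (25% vs 20%) to about 18% with an odds ratio of 1.16 (50% vs 20%). Nothing in the documents shows that calls were or will be influenced by severity; the point is that nothing prevents it. It is worth making as an inexpensive improvement and does not affect the sample size.

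**What to change.** In sections 11.1 and 18:

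1. Send samples and sequence data for interpretation under the study number only, with severity group, bilirubin values and other clinical data withheld.
2. Classify each distinct variant once for the whole cohort, without using the study infants' own jaundice as evidence.
3. Lock the variant classification table before it is merged with the bilirubin groups. This is separate from, and earlier than, the section 13 database lock.
4. State in section 12 whether the between-group comparison counts *unclear significance* or only the two pathogenic classes.

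Keep reporting to families as a separate step that may use full clinical information.

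The cost is protocol wording and a data-flow rule built on study numbers that are already assigned. The documents do not say who interprets variants, so any added workload cannot be judged from them. The downside is that a few research calls may differ from the clinical report.
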